#### Outcomes {12}

Besides long-term digital follow-up, patient-reported and clinical measures will be recorded at 5 possible time points; at baseline and months 1, 3, 5, and 8. Weekly monitoring will be done from baseline to month 5. Imaging will be performed at enrollment and at months 3, 5, and 8. Long-term patient-reported follow-up is planned for 1, 2, and 4 years after enrollment. All data, besides text-message, ultrasound images, and sensor-data, will be captured in REDCap (Research Electronic Data Capture, Vanderbilt Universit,y, USA), a logged secure system designed to capture sensitive non-commercial clinical data hosted at Hvidovre Hospital. REDCap contains options for valid values, range checks, data validation, branching, scheduling, and stop-rules to increase data quality. Pain during all clinical tests will be recorded in addition to the primary measure. Ultrasound will be performed during the enrollment visits and again at months 3, 5, and 8. For a visual overview of data collection schedule, see table 11. We have reported our outcomes in a prioritized order in addition to designations as primary, secondary or exploratory, which also reflects the order of hypothesis-testing, analyses, and intentional order of reporting, with all primary and secondary outcomes intended for the primary report. Note that for this reason, the order and count of outcomes below reflect the total number of variables of interest within each outcome. No core outcome set exists for this or similar populations, and the outcomes are chosen based on current literature and clinical experience.

# Table 10. Overview of outcome domains and prioritized hierarchy of outcomes Outcome domain Specific outcome variables

		Primary outcome		
Sport function	1.	KOOS-child 'Sport/play' 0-100 subscale (7 items)		
		Secondary outcomes		
Patient-acceptable Symtom- state	2.	PASS question (Y/N)		
Knee-related Quality of Life	3.	KOOS-child 'Quality of Life' 0-100 subscale (5 items)		
Pain intensity and frequency (Pain flares)	4.	4-week-average episodes of pain flares (≥4 on 0-10 NPRS)	11.	KOOS-child question P1 on 'Pain' subscale (1-5 Likert scale)
	5.	Worst pain past week (0-10 NPRS)	12.	Level of pain/discomfort (EQ-D5-Y 4)
Participation in sports and physical activity	6.	4-week average hours of sports participation	13. 14. 15. 16. 17.	4-week average hours of MVPA Satisfaction with extent of sports participation Pre knee pain level of sports participation Pre knee pain level of physical activity Time to return to sport (week no.)
Osgood-Schlatter morphology (ultrasound imaging)	7.	Flaviis composite severity score	18. 19. 20.	Tendinosis signs (thickening or hyperemia) Infrapatellar bursitis signs (effusion or hyperemia Hyperemia of the tibial tubercle ad modum Öhberg
Pain during knee loading	8.	Anterior Knee Pain Provocation test (0-10 NPRS)	
 
21.
 
22.
 
23.
 
24.
 
25.
 
	Pain during knee extension test (0-10 NPRS) Pressure-pain threshold at the tibial tubercle (kPa) KOOS-child 'Pain' 0-100 subscale (8 items) Known pain during manual palpation Pain during countermovement jump (0-10 NPRS)
Objective knee function			26. 27. 28. 29.	Maximal isometric knee extension strength (Nm/kg) Countermovement jump height (cm) Countermovement power (W) Knee extensor flexibility change (°)
Global rating of change	9.	7-point Likert scale	30.	Satisfaction with treatment (Y/N)
Usual activities	10.	Patient-specific function scale (NRS 0-10)	31.	Problems with usual activities (EQ-D5-Y 3)
Pain beliefs			32.	Kinesiophobia (Tampa Scale of Kinesiophobia, 17 items)
Health			33.	Self-rated health (EQ-D5-Y 0-100 VAS)
		Safety outcomes		
	1.	Any adverse events		

#### **Primary outcome**

#### KOOS-child 'Sport/play' subscale

The primary between-group difference will be evaluated using the KOOS-child (Knee injury and Osteoarthritis Outcome Score – Child), designed specifically for adolescents and youths aged ≥10 years experiencing knee problems. The KOOS-child contains 5 independent subscales with domains 'Pain' (11 items), 'Symptoms' (7 items), 'Activities of Daily Living' (11 items), 'Sport/play' (7 items), and 'Quality of Life' (6 items). The questions are answered on Likert scales from 0 to 4 points and pertains to the prior week. The scoring of each subscale is normalized to a 0-100 score, 0 being extreme symptoms and 100 being no symptoms. Four subscales (excluding 'Activities of Daily Living' due to low responsiveness) will be recorded and presented, but the subscale 'Sport/play' will be prioritized based on study aims and feedback and preferences from patient representatives and will thus provide properties for sample size calculation. The four included subscales have low detectable change on the group level (1.86-2.66 points), acceptable standard error of measurement (5.69-8.14 points), and substantial/near-perfect test-retest reliability (ICC 0.78-91).

#### Secondary and exploratory outcomes

#### Patient Acceptable Symptom State

The question pertaining to Patient Acceptable Symptom State (PASS) is designed in collaboration with patient representatives. The recall period will be one week, and the outlook period a 'few months' as in previous applications in musculoskeletal conditions with fluctuating symptoms. The phrasing of the PASS will be (approximate English translation): "If you consider your knee pain during the past week, and how it affects your ability to do activities of daily living (for example participating in school, in sports, and socially), would you consider your current symptom state acceptable for the next few months?". The proportions of yes/no in each group will be captured and compared at designated time points.

#### KOOS-child Quality of Life', 'Symptoms' and 'Pain' subscales

The above subscales will be collected and change scores compared in the same manner as the primary 'Sport/play' subscale.

#### Frequency and intensity of pain flares

A pain flare in this study is defined as any time a participant reports episodes of pain of NPRS ≥4 through weekly monitoring. As an outcome, a 4-week median of number of pain flares during week 19-22 (frequency of pain flares) and the worst pain the past week at week 22 (intensity of pain) will be calculated and

compared. In adult populations with knee pain, the 0-10 numerical pain rating scale has shown near-perfect test-retest reliability of ICC 0.95 and low detectable change of 1.33 points. Frequency will also be captured using the P1 question from the KOOS-child 'Pain' subscale: "During the past month, how often have you experienced knee pain?" with potential responses "Never" (1), "Rarely" (2), "Sometimes" (3), "Often" (4), "All the time" (5). Finally, participants will rate their problems with Pain/Discomfort in the 3-point Likert EQ-D5-Y.

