#### Participation in sports and physical activity

According to WHO recommendations, a daily minimum of 60 min of moderate to vigorous physical activity (MVPA, such as biking, running/exercising/high-intensity training) is needed to stay healthy for 5-17-yearolds. Thus, being at either under or above this cutoff during a 4-week average from week 18-22 will be assessed, in addition to a continuous comparison between the two groups of minutes of MVPA during the same time period. Self-reported levels of physical activity are highly under-reported from trials-participants, and sensors increase the precision. Minutes of MVPA will be captured using waterproof threeaaxis12 Hz accelerometers (SENS®, Copenhagen, Denmark) applied once to the participant's thigh during the enrollment visit using an adhesive patch (35 cm^2, 8 g). The sensors have shown 92±5% discriminate agreement when distinguishing between different activities (light sleep, deep sleep, lying/sitting, standing, sporadic walking/slow biking, walking, biking, running/exercising/high-intensity training). Physical activity data will also allow posthoc analyses of exposure.

In addition to physical activity, the level of participation in sports will be captured through weekly monitoring. Participants will be asked how many hours they have been participating in sports in the preceding week. Return to sport time will be defined as the first week participating in sports, followed by one more week also with sports participation. Participants will also be asked during clinical visits if their return to sport was at their pre-injury level or less/more and if they are satisfied with the current extent of their sports participation.

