## Sample size considerations {14}

The properties of the primary outcome measure KOOS-child and the "Sport/rec" subscale have been well investigated, with a validation study including adolescent participants with Osgood-Schlatter amongst other overuse- and acute knee disorders. A small cohort of patients in our clinic (n=16) who 1) were eligible for inclusion in the trial at baseline, 2) received the intervention in question and 3) attended follow-up, reported their global rating of improvement on a 7 point Likert scale ranging from 'much worse (7)' to 'much better (1)'. Patients who reported 'much better (1)' or 'better (2)' had a mean improvement on KOOS-child

'Sport/play' subscale of 12.7±16 points, whereas patients reporting less improvement ('little' improvement or 'no change') only had a 3.57 point increase. In absence of more robust specific data in terms of severity, intervention, and length of follow-up, we will utilize this 9 point difference as a threshold for determining superiority. We consider this to be a meaningful change and a relevant between-group difference, and is within the recommended range of 8-10 points (heartbeat-med.com/resources/knee-injury-and- osteoarthritis-outcome-score-koos). This change also exceeds the smallest detectable group-level change (2.66 points) and the standard error of measurement (8.02 points).

In order to detect such a change with a standard deviation of 16 points an  $\alpha$  level (type I/false positive error rate) of 5% and power ( $\beta$ -1, or probability of avoiding type II/false negative error rate) of 90%, 55 (54.8) participants per group would be needed based on an independent one-sided t-test (R 4.0.2, Foundation for Statistical Computing, Vienna, Austria; RStudio 1.0.153, power.t.test package). To account for a potential 15% dropout rate a total of 130 participants will be included.

This will correspond to a 0.56 Cohens d 'medium' effect size at 90% power (figure 3). The smallest effect size reliably detectable will thus be >0.482 (Cohens d 'small' effect size) at  $\geq$ 80% power (Jamovi 1.2.25, jpower module), surpassing the trivial (<0.2) and small (>0.2) effect size thresholds. We also consider this sample size to be operationally feasible within the given timeframe and with the resources available to our group.

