We will employ a similar analysis strategy for other numerical outcome variables. For non-numeric variables, differences between groups will be analyzed by logistic regression models, and non-normally distributed residuals for ratio-interval scale outcomes will be compared by non parametric boot strap tests. To supply detailed trajectories and inferences of treatment response over time, we will fit mixed-effects models for the imaging outcomes (months 0, 3, 5, 8); time-to-return to sport, weekly hours of sports participation, pain-flares, and sensor-based physical activity (weeks 0 to 22); clinical outcomes (months 0, 1, 3, 5, 8); and remaining patient-reported outcomes (months 0, 1, 3, 5, 8, 12, 24, 48).

Mean and SD values will be reported if data appear approximately normally distributed. If data are nonnormally distributed, they will be presented as median and interquartile range (IQR). We will report 95% confidence intervals, exact p-values to the third decimal, and discussions of minimal detectable change (MDC) and minimal important change (MIC) when relevant/possible. Frequency data will be reported as "No. (%)".

Our standard option for all variables, is to be analyzed with the highest resolution possible, meaning no collapsing or dichotomization to retain as much information as possible in the dataset. However, some assessor-dependent scales, such as ultrasound scoring of the (non-normal maturation-related) fragmentation quality of the tibial tubercle bone, contains the potential values "none" (1), "unclear", (2), "little", or "apparent/extensive" (4). The same applies to some other ultrasound measures and clinical examination findings. Depending on the distribution of responses into these categories, we might choose to exclude data from the "unclear" category or collapse the "little" and "apparent/extensive" categories if we estimate the number of responses to be too low to make meaningful inferences.

Once the primary data have been analyzed, we will also compute and report the RCT-Fragility Index (how

many patients would need to change from success to non-success to render the potential experimental effect non-significant or equal) based on the PASS outcome for easier clinical interpretation of the robustness of results.

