# Appendix 4: Weekly monitoring via text-messages (Danish)

[figure not shown]
[figure not shown]

Figure 10. Flow of text-based monitoring in the usual care group from week 0 to 22	
Question 1	
Hvor mange timer vil du sige, at du i alt har deltaget i sport, i sidste uge (uge <previous_week_number>)? Det gælder også sport i forbindelse med idrætsundervisning, i skolegården, eller i fritiden. 0 = Jeg har ikke dyrket sport overhovedet 1 = 0-30 minutter over hele ugen 2 = 30-60 minutter over hele ugen 3 = 1-2 timer over hele ugen 4 = 2-3 timer over hele ugen 5 = 3-5 timer over hele ugen 6 = Mere end 5 timer over hele ugen</previous_week_number>	
Reply	
Question 2	
Hvor mange gange i sidste uge har du oplevet, at dine knæsmerter har været på 4 eller mere, på 0-10 smerte-skalaen (0=ingen smerter, 10=værst tænkelige smerter)? Svar med et helt tal for antal gange.	
Reply	
Question 3	
Hvor mange dage i sidste uge har du lavet din udspændings- øvelse? Svar med et helt tal (0 til 7) for antal dage.	
Reply	
Question 4 Hvor mange dage i sidste uge, har du lavet din balance-øvelse?	
Svar med et helt tal (0 til 7) for antal dage.	
Reply	
Question 5	
Hvilket niveau er du nået til i balance-øvelsen?         1 = Et-bens stand i 30 sekunder         2 = Side-løft         3 = Halv-måner         4 = Side-drej         5 = Supermand         6 = Udfald	
Reply	
End of survey	
Tak for dine svar. Husk at åbne din SENS-app rimelig tit, f.eks. mens du laver dine øvelser. Du skal også huske at skrive ned hvornår du evt. har skiftet plaster.	

[figure not shown]

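### Secondary outcome 4 (pain-flare frequency) is a 4-week average in Tables 1 and 10 but a 4-week median in the outcome text, and nothing says which governs

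*Combined protocol and SAP*

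**What the plan says.** Table 10 ranks pain-flare frequency as outcome 4, the third of the secondary outcomes, and labels it "4-week-average episodes of pain flares (≥4 on 0-10 NPRS". Table 1 lists the same variable in the same terms. Neither table gives a week range.

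The section on frequency and intensity of pain flares defines a flare as "any time a participant reports episodes of pain of NPRS ≥4 through weekly monitoring" and sets the outcome as "a 4-week median of number of pain flares during week 19-22". Appendix 4 shows the raw data in the usual-care text-message flow. Participants are asked how many times in the past week their knee pain reached 4 or more, and must answer with a whole number ("Svar med et helt tal for antal gange"). The input is therefore one count per week.

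Two other statements bear on the choice. The statistical methods section sets a default of analysing variables at the highest resolution, "meaning no collapsing or dichotomization to retain as much information as possible in the dataset". It also plans mixed-effects models for several weekly series, including "pain-flares, and sensor-based physical activity (weeks 0 to 22".

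**The concern.** A mean and a median of four counts are different statistics, so the outcome cannot be computed from the plan as written. The Outcomes section says that the listed order is the order of hypothesis testing and that all secondary outcomes are meant for the primary report. The section on error rates relies on that order as its reason for not adjusting for multiplicity by default. That argument needs each ranked outcome to have one definition. With two in force, the choice could be made after the data are seen, which is the flexibility that the protocol says pre-registration is meant to remove.

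The median also has a specific weakness for this construct. It ignores how bad the worst week was, and it is zero for anyone whose flares all fall in one of the four weeks.

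**Working it through.** **No figure to reproduce.** The documents give no expected rate, variance, effect size or power for pain flares. The sample size rests on KOOS-child 'Sport/play' alone ("participants per group would be needed based on an independent one-sided t-test"). All flare rates and dispersions below are assumptions.

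**Step 1: can the definitions disagree?** The median of four counts is the average of the second and third ordered values.

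- 0, 0, 0, 7: mean 7/4 = 1.75; median (0+0)/2 = 0.
- 0, 0, 2, 4: mean 6/4 = 1.5; median (0+2)/2 = 1.
- 0, 0, 1, 1: mean 2/4 = 0.5; median (0+1)/2 = 0.5.

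They can. The median is 0 exactly when at least three of the four weeks are flare-free. The mean is 0 only when all four are.

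**Step 2: how often does a participant with flares score 0?** Let p0 be the probability of a flare-free week, with weeks independent. Then P(at least one flare and median 0) = 4·p0³·(1−p0), and P(at least one flare) = 1 − p0⁴. For Poisson counts with weekly rate m, p0 = exp(−m). At m = 1, p0 = 0.368, so the share is 0.126/0.982 = 13%.

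If rates vary between people as a gamma with mean m and shape s, P(k given weeks all flare-free) = (1 + k·m/s)^(−s). The numerator becomes 4·[(1+3m/s)^(−s) − (1+4m/s)^(−s)] and the denominator 1 − (1+4m/s)^(−s). At m = 1 and s = 1 this is 4·(1/4 − 1/5) = 0.20 over 1 − 1/5 = 0.80, or 25%. Simulation of 400,000 participants per setting gives the same values.

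Share of participants with at least one flare who score 0 on the median:

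| Assumed mean rate per week | Poisson | Gamma s = 0.5 | s = 1 | s = 2 |
|---|---|---|---|---|
| 0.25 | 66% | 52% | 57% | 61% |
| 0.5 | 41% | 38% | 40% | 41% |
| 1 | 13% | 27% | 25% | 22% |
| 2 | 1% | 18% | 14% | 9% |

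Under the mean this share is 0% at every rate.

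These values assume no clustering of flares by week within a person. Clustering raises them. At 1 per week with s = 1, the share of *all* participants with a flare but a median of 0 is 20% with no clustering, 26% with a weekly gamma factor of shape 1, and 30% with shape 0.5.

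**Step 3: illustrative power at 55 per arm, one-sided 5% t-test, mean versus median.**

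40% rate reduction, no week-to-week clustering:

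| Control rate per week | s = 1 | s = 2 |
|---|---|---|
| 0.5 | 65% vs 59% | 78% vs 70% |
| 1 | 75% vs 71% | 91% vs 87% |
| 2 | 79% vs 77% | 95% vs 94% |

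2 versus 1 flares per week, s = 1, by week-to-week clustering:

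| Weekly gamma shape | Difference seen by the median (true 1.0) | Power, mean vs median |
|---|---|---|
| none | 1.01 | 95.2% vs 94.6% |
| 4 | 0.95 | 93% vs 92% |
| 2 | 0.91 | 92% vs 90% |
| 1 | 0.84 | 88% vs 84% |
| 0.5 | 0.71 | 79% vs 69% |

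Repeat runs agree to within about two points. The loss runs from 0.6 points (95.2 − 94.6) to 10 points (79 − 69).

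**The case against.** The best defence is that the harm is limited. A median describes a typical week and is a legitimate summary. The weekly mixed-effects model uses every count from week 0 to week 22, and the same outcome section adds worst pain at week 22 and a KOOS-child item on pain frequency. The trial was not sized on this outcome. One could also say that the text is more detailed than the tables and should be taken as governing, with 'average' used loosely. Most of this stands as a limit on the damage. It does not resolve the conflict: no section gives the text precedence or equates average with median, and the mixed model does not say which month-5 summary is tested.

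A reader might infer three stronger things that the documents do not support.

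- *That the median zeroes out many participants with flares.* This is true if flares are infrequent by weeks 19-22 and not if they are common. The documents give no rate.
- *That the median costs a definite amount of effect or power.* Any single figure depends on the assumed week-to-week dispersion. With none, in the 2 versus 1 scenario, the difference is not attenuated and power is about 95% either way.
- *That the physical-activity window is also wrong*, because it is described as "during a 4-week average from week 18-22", which is five weeks if counted inclusively. The Compliance criteria section counts weeks 4-13 as nine and weeks 0-13 as thirteen. On that convention weeks 18-22 are four, matching the label. The flare window counts four separate weekly texts, 19 to 22. This is a difference in notation, not an error.

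**Conclusion.** The contradiction is real and sits in the current text: average in two tables, median in the outcome section, for a ranked secondary outcome intended for the primary report. That the two can give different values follows from arithmetic and needs no assumption.

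The size is conditional. About four in ten participants with flares would score 0 under the median at 0.5 flares per week, 13-27% at 1 and 1-18% at 2. These figures assume Poisson counts given each person's rate, with or without gamma variation between people, and no clustering by week. Power loss from under 1 to about 10 points is illustrative only. The point should be fixed, but it does not touch the primary outcome or the sample size.

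**What to change.** Before unblinding, replace the median in the pain-flare section with the mean weekly number of flares over weeks 19-22, which is the total divided by the number of weeks answered. State the same definition and window in Tables 1 and 10. This agrees with both tables as they stand, keeps every reported episode, and fits the plan's rule on resolution.

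A count model, such as negative-binomial regression with an offset for weeks answered, would suit these data but is optional. The reconciliation does not depend on it.

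The cost is wording in three places, recorded as a dated amendment. No data collection changes. The Trial status section reports inclusion complete at 130 of 130, so the date of the change relative to unblinding should be documented.

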#### Participation in sports and physical activity

According to WHO recommendations, a daily minimum of 60 min of moderate to vigorous physical activity (MVPA, such as biking, running/exercising/high-intensity training) is needed to stay healthy for 5-17-yearolds. Thus, being at either under or above this cutoff during a 4-week average from week 18-22 will be assessed, in addition to a continuous comparison between the two groups of minutes of MVPA during the same time period. Self-reported levels of physical activity are highly under-reported from trials-participants, and sensors increase the precision. Minutes of MVPA will be captured using waterproof threeaaxis12 Hz accelerometers (SENS®, Copenhagen, Denmark) applied once to the participant's thigh during the enrollment visit using an adhesive patch (35 cm^2, 8 g). The sensors have shown 92±5% discriminate agreement when distinguishing between different activities (light sleep, deep sleep, lying/sitting, standing, sporadic walking/slow biking, walking, biking, running/exercising/high-intensity training). Physical activity data will also allow posthoc analyses of exposure.

In addition to physical activity, the level of participation in sports will be captured through weekly monitoring. Participants will be asked how many hours they have been participating in sports in the preceding week. Return to sport time will be defined as the first week participating in sports, followed by one more week also with sports participation. Participants will also be asked during clinical visits if their return to sport was at their pre-injury level or less/more and if they are satisfied with the current extent of their sports participation.

